**3. Source:**

a) Identify the source of the drug, device or biologic to be used.

All study medications will be purchased from appropriate vendors through the Investigational Pharmacy of YNHH.

b) Is the drug or device provided free of charge?  Yes  No

If yes, by whom?

**4. Preparation and Use:** Describe the method of preparation, storage, stability information, and for parenteral products, method of sterilization and method of testing sterility and pyrogenicity. NA

**5. Use of Placebo: x Not applicable to this research project**

This is not a treatment trial. We need a placebo condition to identify the individual versus combined effects of naltrexone and the glutamatergic agents (memantine or NAC).

Provide a justification which addresses the following:

a. Describe the safety and efficacy of other available therapies (if any). This is not a treatment trial or a treatment seeking population of heavy drinkers

- b. State the maximum total length of time a participant may receive placebo while on the study. 16 days
- c. Address the greatest potential harm that may come to a participant as a result of not receiving effective therapy (immediate or delayed onset.) Not a treatment seeking population
- d. Describe the procedures that are in place to safeguard participants receiving placebo. Not a treatment seeking population

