In the current proposal we would like to conduct an important extension of this work. We will test the hypothesis that by targeting both opioidergic and glutamatergic mechanisms, one may synergistically target multiple neurochemical and behavioral processes, leading to optimal reduction of alcohol drinking. This pilot trial will be conducted in FHP drinkers in whom we have observed reduction in alcohol reward with MEM and in alcohol drinking with NTX. We will test the efficacy and tolerability of the combined use of MEM and NTX. We will also test the efficacy and tolerability of the combined use of N-acetyl cysteine and NTX. N-acetylcysteine (NAC), an acetyl pro-drug of cysteine is another agent which can be used to target the glutamatergic system. NAC is believed to produce its effects by stimulating the cysteine-glutamate exchanger and thus altering synaptic glutamate levels. A significant potential advantage of NAC is better tolerability, which may make it a better glutamate-altering agent to use in combination with NTX. Finally, we will also evaluate the predictive utility of impulsive responding, implicit alcohol motivational tendencies, and variations in genes for opiate receptors and for signal transduction proteins linking dopamine and glutamate receptors upon alcohol drinking behaviors.

The following specific aims will be tested:

**Primary Aim 1:** Evaluate the effects of pretreatment with a combination of naltrexone (NTX; 50 mg) and memantine (MEM; 20 mg) or N-acetylcysteine (NAC; 2400 mg) on drinking in FHP drinkers.

*Primary Hypothesis:* Combination treatment with NTX and MEM or NAC, when compared with NTX alone, will reduce number of drinks consumed during the self-administration period.  
*Exploratory hypothesis:* Combination treatment with NTX and MEM will reduce time to first drink and increase the average time to consume each drink, during the self-administration phase.

**Primary Aim 2:** Evaluate the effects of pretreatment with a combination of naltrexone (NTX; 50 mg) and memantine (MEM; 20 mg) or NAC (2400 mg) on alcohol craving in FHP drinkers  
*Hypothesis:* Combination treatment with NTX and MEM or NAC, when compared with NTX alone, will reduce alcohol craving (Yale Craving Scale) during the self-administration period  
*Exploratory hypothesis:* Combination treatment with NTX and MEM will reduce craving in response to the alcohol cue presented just prior to the priming drink period.

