This project will use a within-subjects, crossover design to examine the effects of naltrexone with or without memantine or NAC on drinking and other alcohol-related behavioral measures in alcohol-dependent or abusive heavy drinkers with a positive family history of alcoholism (FHP). Non-treatment-seeking heavy drinkers will participate in three ADP lab sessions, occurring prior to medication and after the first and second weeks of medication treatment. They will also participate in two follow-up appointments at one week and one month after participation. The baseline ADP will be used to familiarize subjects with the laboratory procedures and reduce order effects in the subsequent ADP sessions. Each ADP will involve consumption of a priming alcoholic drink (0.03 mg%) at 3 pm followed by three one-hour choice drinking periods. During each hour subjects will choose between 4 alcoholic drinks (0.015 mg% each) or equivalent monetary rewards (\$3 per drink). During each 6-8-day medication outpatient treatment period (up to 13 days), subjects will receive naltrexone and be randomized to receive either 20 mg of memantine, 2400 mg of NAC or placebo, and medication doses will be tapered up and adverse events recorded on a daily basis.

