***Justification for choice of naltrexone dose:***

We will use naltrexone in a dose of 50 mg/day. This is the dose of naltrexone that is FDA approved for the treatment of alcohol dependence and has been most commonly used in most clinical trials (Anton et al., 2005; O'Malley et al., 1992; Volpicelli et al., 1992) and laboratory studies (Davidson et al., 1999; O'Malley et al., 2002; Anton et al., 2004). This dose also produces complete blockade of the mu-opioid receptors (Weerts et al., 2008). The 100 mg/day dose has also shown efficacy in many recent clinical trials (e.g., Anton et al., 2006), and our own preliminary evidence suggests that this dose may produce greater reduction in drinking in FHP drinkers than the 50 mg dose. However, in the proposed "proof of concept" trial we did not want to run the risk of missing the signal for a synergistic effect of memantine or NAC by combining it with a dose of naltrexone, which had a large effect of its own. Moreover, now that we are combining two medications we want to use a lower dose of naltrexone to minimize side effects from the combined pharmacotherapy.

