#### Study Medication (Naltrexone/Memantine/NAC) Administration and Stabilization: 6-8 Days

All subjects will receive naltrexone treatment and be randomly assigned to receive either memantine 20 mg, NAC 2400 mg or placebo for seven days as outpatients. The randomization schedule will be generated by the Data Management and Biostatistics Component statisticians and provided to the pharmacist. They will take the final dose of 50 mg NTX + 20 mg MEM or 2400 mg NAC or placebo, when they will complete the alcohol self-administration paradigm described below. Doses of naltrexone and memantine will be tapered up as follows

GROUP	Day 1	Day 2	Day 3	Day 4	Day 5	Days 6-8 (up to 13)
Naltrexone	25 mg	50 mg	50 mg	50 mg	50 mg	50 mg
Memantine/ NAC/placebo	0/0/0 mg	0/0/0 mg	5/600/0 mg	10/1200/0 mg	20/1200/0 mg	20/2400/0 mg

Subjects will come to our clinic each day to take their medications at 10 am. During these appointments they will complete assessments. These procedures will 1) ensure compliance with medication administration, 2) monitor side effects during naltrexone and memantine/nacetylcysteine dose escalation, and 3) monitor tolerability of naltrexone, memantine, and NAC co-administration. ***During this period, subjects will be asked to continue normal drinking behavior similar to the procedures used in our preliminary studies.***

In the event that a subject cannot come to the clinic daily, other arrangements will be made, such as giving the participant more than one dose of their medication at a time and using a daily phone call as both a reminder to take the medication and as a means to monitor adverse events. We will allow this up until the final two doses of medication prior to the ADP. This arrangement will be determined by the investigator and her staff based on the participant's other obligations and compliance.

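### Naltrexone is given in every medication period, so the trial can estimate only what memantine or NAC adds to it; the claims about synergy and individual effects go beyond the design

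*Combined protocol and SAP*

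**What the plan says.** Three places describe what the trial is meant to show.

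- Section V, item 1 (Statement of Purpose) offers as the hypothesis to be tested that, by acting on both the opioid and the glutamate system, "one may synergistically target multiple neurochemical and behavioral processes, leading to optimal reduction of alcohol drinking".
- Section V, item 3, in the justification of the naltrexone dose, gives as one reason that the investigators wished to avoid "missing the signal for a synergistic effect of memantine or NAC".
- Section VI, item 5 (Use of Placebo) states: "We need a placebo condition to identify the individual versus combined effects of naltrexone and the glutamatergic agents", and names memantine and NAC as those agents.

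Two places describe the treatments. The Research Plan says that in each medication period "subjects will receive naltrexone and be randomized to receive either 20 mg of memantine, 2400 mg of NAC or placebo". The Study Medication section repeats it: "All subjects will receive naltrexone treatment and be randomly assigned to receive either memantine 20 mg, NAC 2400 mg or placebo". Its dose table has one naltrexone row and no placebo naltrexone. The only session without naltrexone is the baseline alcohol-drinking session, held before any medication and intended to familiarize subjects with the procedures.

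The hypotheses under Primary Aims 1 to 3 compare the combination with NTX alone. The models in Section V, item 4 (Statistical Considerations) have one treatment factor with that same contrast. None contains a naltrexone factor or a drug-by-drug interaction.

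**The concern.** Separating individual from combined effects, or showing synergy, requires observing each agent without the other. No medication period does this for memantine or NAC, so the placebo condition cannot serve the purpose given for it, and the stated test of synergy has neither a design nor an analysis behind it.

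This matters because the protocol itself reports effects of memantine without naltrexone in family-history-positive drinkers. Section V, item 1 and the Background describe reduced stimulation and craving with modest reductions in drinking, and the memantine dose justification describes similar findings at the dose used here. If drinking is lower on NTX+memantine than on NTX alone, memantine's own effect is a live explanation. For NAC the Background says its influence on alcohol behaviors had not been tested, so the documents offer no NAC-alone comparison even from outside the trial.

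**Working it through.** The question is which effects the design identifies. The plan's only sample-size figure, 30 completers as 3 × 10 (Power Analysis), does not bear on it.

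**Set-up.** Write the mean outcome in a condition as

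μ + a·NTX + b·MEM + c·NAC + d·(NTX×MEM) + e·(NTX×NAC),

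where each drug indicator is 0 or 1. Here a, b and c are the individual effects, and d and e are the interactions, that is, synergy or its opposite. There are 6 parameters.

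**Randomized conditions** (Research Plan; Study Medication section):

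- NTX+placebo: μ + a
- NTX+MEM: μ + a + b + d
- NTX+NAC: μ + a + c + e

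The available contrasts are

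- NTX+MEM minus NTX+placebo = b + d (memantine add-on)
- NTX+NAC minus NTX+placebo = c + e (NAC add-on)
- their difference = (b + d) − (c + e)

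b and d appear only as a sum, as do c and e. Suppose the memantine add-on equals s. Then (b = s, d = 0) is purely additive, (b = 0, d = s) is pure interaction, and (b = 2s, d = −s) is sub-additive. All three predict identical data. Each two-drug interaction needs four cells (neither drug, NTX, agent, both); only two are observed on medication.

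**Rank check.** A contrast is estimable if adding it to the design matrix leaves the rank unchanged.

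| Design | Rank | Two add-on effects | NTX vs no drug | MEM alone, NAC alone | Both interactions |
|---|---|---|---|---|---|
| A. Randomized conditions only | 3 of 6 | yes | no | no | no |
| B. A plus unmedicated baseline, no session effect assumed | 4 of 6 | yes | yes | no | no |
| C. A plus baseline, session effects free | 5 of 8 (6 + 2 session terms) | yes | no | no | no |
| D. Full 2 × 3 layout, for comparison | 6 of 6 | yes | yes | yes | yes |

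Row C takes each condition to occur in both medication periods. The plan does not list the sequences, but no allocation of these three conditions can supply the missing cells.

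**Cost of making synergy estimable.** With equal independent cells of size n, an add-on contrast has variance 2σ²/n and an interaction contrast 4σ²/n, so the interaction needs twice the n per cell. The documents give no effect size or SD. For assumed standardized effects of 0.5, 0.8 and 1.0 (two-sided 0.05, 80% power), n per cell is 63, 25 and 16 for the add-on and 126, 50 and 32 for the interaction. These figures are for independent groups and show relative cost only.

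**The case against.** The strongest reply is that the planned inference is already right. Every hypothesis under Aims 1 to 3 and every model for them compares the combination with NTX alone, and no synergy test is specified. This stands. A reader might infer from the synergy wording that the primary analysis is mis-specified; it is not.

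A second reply is that the placebo sentence can be read narrowly, with NTX+placebo as the individual agent and NTX plus a second agent as the combination. That would be enough if the sentence spoke only of naltrexone, but it names the glutamatergic agents too. Its place in an ethics-form field marked not applicable lowers its prominence without making it correct.

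A third is that synergy is meant as mechanism. That is partly fair for the Statement of Purpose, which the formal aims then make operational as an add-on comparison. But the text introduces it as a hypothesis under test, the dose justification speaks of detecting its signal, and the supporting rat experiment is one in which memantine strengthened the effect of a low naltrexone dose, which is an interaction claim.

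A fourth is that the baseline session is drug-free, and Section IX, item 2 refers to change in drinking from the first session to the later two. This also stands, as a limit on the point: it would be too strong to say the trial offers no view of naltrexone's own effect. It offers an uncontrolled before-and-after view, interpretable only if session effects are absent.

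Two further readings are tempting and unsupported. One is that a positive result would be reported as synergy. The documents announce no such conclusion: the analysis section ties support for the hypothesis to the comparison with NTX alone, the Potential Benefits item speaks of an initial efficacy signal for the combination, and the Power Analysis presents the trial as a pilot for tolerability and effect-size estimates. The other is that such a result would fit an independent effect and synergy equally well. Nothing in the documents weighs the two; an independent effect is simply also a possible explanation.

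**Conclusion.** The point holds as a mismatch between three statements of purpose and the design. The randomized conditions identify two add-on effects over NTX and their difference. Memantine alone, NAC alone and both interactions are unidentified, and more subjects would not change that. NTX against no drug is visible only through a non-randomized first session confounded with order.

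The result rests on the conditions as the Research Plan and Study Medication section list them, with naltrexone in all three, and on no distributional or effect-size assumption. The aims' hypotheses, the models and the sample size are unaffected. What is at issue is how far the conclusions may reach.

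**What to change.** 1. In Section VI, item 5, state that NTX+placebo is needed to identify the add-on effect of memantine or NAC over NTX.
2. In Section V, item 1 and in the naltrexone dose justification, replace synergy as something this trial tests or detects with an add-on effect over NTX. Synergy may remain as background rationale. The dose itself is not in question here.
3. In Section V, item 4, add that a reduction relative to NTX alone is also consistent with an independent effect of memantine or NAC, so synergy cannot be concluded from this trial.

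The cost is a slightly less ambitious claim. No arm, dose, visit or model changes.

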**6. Use of Controlled Substances:**

Will this research project involve the use of controlled substances in human subjects?

Yes  No See instructions to view controlled substance listings.

If yes, is the use of the controlled substance considered:

Therapeutic: The use of the controlled substance, within the context of the research, has the potential to benefit the research participant.

Non Therapeutic: Note, the use of a controlled substance in a non therapeutic research study involving human subjects may require that the investigator obtain a Laboratory Research License. Examples include controlled substances used for basic imaging, observation or biochemical studies or other non-therapeutic purposes. See Instructions for further information.

**7. Continuation of Drug Therapy After Study Closure  Not applicable to this project**

Are subjects provided the opportunity to continue to receive the study drug(s) after the study has ended?  Yes  No

If yes, describe the conditions under which continued access to study drug(s) may apply as well as conditions for termination of such access.

**SECTION VII: HUMAN SUBJECTS**

**1. Recruitment Procedures:** How will potential subjects be identified, contacted and recruited? Attach copies of any recruitment materials that will be used.

- Flyers  Internet/Web Postings  Radio
- Posters  Mass E-mail Solicitation  Telephone
- Letter  Departmental/Center Website  Television
- Medical Record Review  Departmental/Center Research Boards  Newspaper
- Departmental/Center Newsletters  Web-Based Clinical Trial Registries
- Other (describe): use of promotional materials in community (e.g., magnets)
- Clinicaltrials.gov Registry (do not send materials to HIC)

**1a. Assessment of Current Health Provider Relationship for HIPAA Consideration:**

Does the Investigator or any member of the research team have a direct existing clinical relationship with any potential subject?

- Yes, all subjects
- Yes, some of the subjects
- No

If yes, describe the nature of this relationship.

**2. Subject Population** Provide a detailed description of the targeted involvement of human subjects for this research project.

86 healthy heavy drinkers who are not currently seeking treatment for their drinking behavior, between 21-55 years of age.

3. **Inclusion/Exclusion Criteria:** What are the criteria used to determine subject inclusion or exclusion? How will eligibility be determined, and by whom?

Inclusion criteria:

- 1) Ages 21-55
- 2) Able to read English at 6th grade level or higher and to complete study evaluations
- 3) Meet DSM-IV criteria for alcohol dependence or abuse (assessed using the SCID)
- 4) Family history criteria (assessed using the FHAM; see Assessment section)  
Family history positive subjects: At least one first-degree relative with alcoholism as determined by the FHAM  
Family history negative subjects: No first degree relative with alcoholism and no 2nd degree relative with alcoholism unless the participant cannot answer details about the 2nd degree family member's drinking consequences on the FHAM.  
(Average weekly alcohol consumption of standard drinks of at least 25-70 drinks for men and 20-65 drinks for women)
- 5) No more than 3 days abstinence/week in order to maximize the likelihood that subjects will choose to drink during the laboratory sessions

Exclusion criteria:

- 1) Individuals who are seeking alcohol treatment or have been in alcohol treatment within the past 6 months
- 2) Current DSM-IV dependence criteria for other substances, other than nicotine
- 3) Positive test results at more than one baseline appointment on urine drug screens conducted for opiates, cocaine, benzodiazepines, and barbiturates
- 4) Regular use of psychoactive drugs including anxiolytics and antidepressants
- 5) Psychotic or otherwise severely psychiatrically disabled; scores above 2 SD of the mean on the Wisconsin Psychosis Proneness scale
- 6) Medical conditions that would contraindicate the consumption of alcohol
- 7) Medical conditions that would contraindicate the use of naltrexone such as hepatic dysfunction
- 8) Medical conditions that contraindicate the use of memantine or NAC such as asthma, seizures, kidney disease, repeated urinary tract infections, or liver disease
- 9) Individuals taking medications that might interact with memantine, including amantadine or rimantadine; dextromethorphan; carbonic anhydrase inhibitors such as acetazolamide, dichlorphenamide, or methazolamide; or potassium citrate
- 10) Any history of neurological trauma or disease, delirium, or hallucinations, or hepatic, cardiovascular, metabolic, endocrine, or gastrointestinal disease
- 11) Subjects who at any intake appointment have a Clinical Institute Withdrawal Assessment Scale score of 8 or greater, or who report any history of significant or repeated alcohol withdrawals will be excluded from the study and referred for standard alcohol detoxification. This is to reduce the likelihood that subjects enrolled in the study will experience withdrawal symptomatology if they reduce their drinking.
- 12) Women who are pregnant, nursing, or refuse to use a reliable method of birth control; urine pregnancy tests will be completed at intake and prior to administration of alcohol
- 13) Subjects who report disliking spirits will be excluded because hard liquor will be provided during the alcohol administration components of the study.
- 14) Subjects who have taken Naltrexone within 3 weeks immediately preceding admission to the treatment period, all other investigational drugs will require a 4 week washout period.

- 15) Subjects who report any use during the 30 days prior to randomization of the following: anxiolytics, beta blockers, central nervous system stimulants, hypnotics, non-therapeutic doses of neuroleptics and antidepressants, drugs with psychotropic activity, or drugs which cause excessive sedation
- 16) Subjects who have donated blood within the past six weeks

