***Procedures***

**Recruitment, Baseline Assessments, Physical Exam and PIT Task**

Potential subjects will be recruited as described earlier. Participants will be scheduled for an appointment at the Substance Abuse Center in the Connecticut Mental Health Center or at the

Substance Abuse Treatment Unit, New Haven, CT, where informed consent will be obtained prior to any other procedures. Then the intake battery will be administered to assess eligibility for the study. At this intake appointment FH of alcoholism will be assessed using the FHAM (see assessments section, below). The research assistant will schedule a physical exam (including EKG) and routine laboratory work, and hepatic, kidney, and thyroid function tests will be conducted by an APRN. A detailed medical history will be obtained from all subjects and pregnancy tests for all females. Subject characteristics and medical history will be reviewed by the PI to ensure that the subject meets all the eligibility criteria. The subjects will then be scheduled to meet with the study physician ([name]), who will also review their eligibility for the study and review their medical history information and EKG. If eligible to participate, and if they have also consented to participate in the genetic study, we will draw plasma samples for this purpose. For those participants without the use of a phone or cell phone and may be difficult to reach for the next 20 appointments after the initial intake, we will provide them with a disposable study cell phone to enhance communication and attendance at all appointments. Urine will be collected to test for drugs and ethylglucuronide, a metabolite of ethyl alcohol that will be used as a biomarker of alcohol consumption at baseline and the ADP sessions.

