nausea and vomiting. Other, less frequent side effects include nervousness, dizziness, headaches, blurred vision, low energy, fatigue, sleepiness, joint and muscle pain and insomnia. Hepatotoxicity, the most serious potential side effect, has been shown in studies using very high doses of naltrexone (1400 to 2100 mg per week). At the doses used in this study naltrexone has not been reported to produce hepatotoxic effects. However, we will monitor liver function tests prior to the study and exclude individuals with evidence of significant hepatocellular injury (AST, ALT  $>3$ x normal established in pregnant and nursing women, they will be excluded from participation. Naltrexone can also precipitate or exacerbate opiate withdrawal, as a result subjects with abuse or dependence on opiates will be excluded from the study on the basis of self-report and urine drug screens.

Since naltrexone is an opiate antagonist, alternative nonopioid methods of analgesia can be used. In an emergency situation requiring opioids, the amount of opioids necessary for analgesia may be greater than usual, and the resulting respiratory depression may be deeper and more prolonged. As a result, a rapidly acting analgesic which minimizes respiratory depression is preferred and the amount of the analgesic administration titrated to the needs of the patient in a setting equipped and staffed for cardiopulmonary resuscitation. As a result, subjects will be given a card showing that they may be receiving naltrexone. This card will provide detailed information to medical personnel describing the special precautions necessary in the event that the subject should require pain management. In addition, this card will have a code number on it that can be used to identify which medication the subject is on. A phone number of the pharmacy and for the physician on call at the Connecticut Mental Health Center will be listed on the card in the event of an emergency in which it is necessary to determine whether the subject is on active naltrexone.

NAC (also known as Acetylcysteine) has been safely used for several decades in adults and children as a long-term treatment for chronic bronchitis. It has been found to be cost-effective to use and generally well tolerated with mild, most commonly gastrointestinal adverse effects. This dose of NAC (2400 mg) was observed to be safe and tolerable in cocaine dependent participants (e.g. Larowe et al., 2006).

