N-acetyl cysteine is also used for preventing alcoholic liver damage; for protecting against environmental pollutants including carbon monoxide, chloroform, urethanes and certain herbicides; for reducing toxicity of ifosfamide and doxorubicin, drugs that are used for cancer treatment; as a hangover remedy; for preventing kidney damage due to certain X-ray dyes; and for human immunodeficiency virus (HIV).

N-acetyl cysteine is safe for most adults. It can cause nausea, vomiting, and diarrhea or constipation. Rarely, it can cause rashes, fever, headache, drowsiness, low blood pressure, and liver problems.

3) Naltrexone

Naltrexone has been shown to have an effect on the embryo in the rat and the rabbit when given in doses approximately 140 times the human therapeutic dose. Naltrexone, an opioid antagonist, is widely used in the treatment of opioid addiction and more recently has been found to be beneficial in the treatment of alcoholism. Numerous studies have found naltrexone use to be safe and rarely associated with toxicity or severe side effects. The most frequent reported side effects are gastrointestinal in nature. Those include epigastric pain, nausea and vomiting. Other, less frequent side effects include nervousness, dizziness, headaches, blurred vision, low energy, fatigue, sleepiness, joint and muscle pain and insomnia. Hepatotoxicity, the most serious potential side effect, has been shown in studies using very high doses of naltrexone (1400 to 2100 mg per week). At the doses used in this study naltrexone has not been reported to produce hepatotoxic effects. However, we will monitor liver function tests prior to the study and exclude individuals with evidence of significant hepatocellular injury (AST, ALT  $>3$  times normal established in pregnant and nursing women, they will be excluded from participation. Naltrexone can also precipitate or exacerbate opiate withdrawal, as a result subjects with abuse or dependence on opiates will be excluded from the study on the basis of self-report and urine drug screens.

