Effective screening will exclude all subjects who would be at greater risk for complications because of medical, neurological or psychiatric illnesses. Individuals currently dependent on other drugs will be screened out. Subjects maintained on memantine study medication will be issued "keyed" cards which allow health professionals to break the double blind by calling, the Yale-New Haven pharmacy switchboard which answers 24 hours a day. Subjects will also be monitored during daily medication visits for troublesome side effects during the course of the 6 day outpatient period. Although memantine is in FDA category B, there have been few trials where it has been administered to younger women. Therefore, the following precautions will be taken for women: 1) urine pregnancy tests will be performed at intake, prior to starting the medication, and on the day of the alcohol self-administration session. Pregnant or nursing women will be excluded from participation, and encouraged to seek advice about the risk of heavy drinking, encouraged to seek alcohol treatment and if interested referred to other cessation programs; 2) women must agree to use a reliable method of birth control while they are in the study. They will be asked to alert the principal investigator if she departs from her birth control plans or if, in spite of adherence to these plans, she thinks she might be pregnant.

2) Naltrexone:

Effective screening will exclude all subjects who would be at greater risk for complications because of medical, neurological or psychiatric illnesses. Individuals currently dependent on other drugs will be screened out. Subjects who are using opiates will be excluded to avoid any possibility of the subjects experiencing naltrexone precipitated opiate withdrawal. The risk of hepatotoxicity will be minimized by excluding subjects with a history of cirrhosis or significantly elevated liver enzyme tests. Subjects maintained on naltrexone study medication will be issued "keyed" cards which allow health professionals to break the double blind by calling the CMHC pharmacy. Subjects will also be constantly monitored for troublesome side effects during the course of the 12 day outpatient and three days inpatient period.

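### The eligibility list does not carry out the opiate exclusion stated in the naltrexone safety text: a real contradiction with a narrow practical gap

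*Combined protocol and SAP*

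**What the plan says.** The naltrexone safety text gives the rule three times.

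- Section VI.2 (Background Information): "subjects with abuse or dependence on opiates will be excluded from the study on the basis of self-report and urine drug screens".
- Section IX.1 (Risks, Naltrexone) repeats it: "subjects with abuse or dependence on opiates will be excluded from the study".
- Section IX.2 (Minimizing Risks, Naltrexone) sets out two rules, one after the other: "Individuals currently dependent on other drugs will be screened out. Subjects who are using opiates will be excluded to avoid any possibility" of withdrawal precipitated by naltrexone.

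The eligibility list in Section VII.3 is worded differently. Exclusion 2 is "Current DSM-IV dependence criteria for other substances, other than nicotine". Exclusion 3 names opiates, but only excludes people who screen positive at two or more baseline visits. Exclusion 4 concerns regular use of psychoactive drugs. Exclusion 7 is "Medical conditions that would contraindicate the use of naltrexone such as hepatic dysfunction". Exclusion 15 concerns reported use, in the 30 days before randomization, of several drug classes, including psychotropic and heavily sedating agents. It does not name opiates.

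Eligibility is checked twice (Section V.3, Procedures). The PI check is described as "Subject characteristics and medical history will be reviewed by the PI to ensure that the subject meets all the eligibility criteria". The study physician is someone "who will also review their eligibility for the study and review their medical history information and EKG".

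**The concern.** All treatment conditions contain naltrexone, so the opiate exclusion matters for every subject, including those on naltrexone with placebo. Dosing is outpatient. Staff screen against the list in Section VII.3, not against the risk narrative in Sections VI and IX. If the list is looser than the narrative, a reviewer who applies it correctly could pass someone who, according to the safety sections, would be kept out. The stake is the safety of a few people and the internal consistency of a drug-safety exclusion. It is not the analysis.

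**Working it through.** No arithmetic applies. The check sets each rule in the safety text against every listed exclusion: 16 general criteria plus 6 for the PIT task, 22 in all.

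| Stated in the safety text | Where the list could supply it | Does it? |
|---|---|---|
| Opiate dependence excluded (VI.2, IX.1) | Exclusion 2 | Yes |
| Opiate abuse excluded (VI.2, IX.1) | Exclusion 2 | No, dependence only |
| Current opiate use excluded (IX.2) | Exclusions 3, 4, 15 | In part |

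**Step 1: is abuse covered by implication?** No. The list treats the two diagnoses as separate. Inclusion 3 reads "Meet DSM-IV criteria for alcohol dependence or abuse (assessed using the SCID", so the authors named both when they meant both. Of the 22 exclusions, none names opiate abuse and one (exclusion 3) names opiates at all.

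**Step 2: does another criterion close the gap?**
- Exclusion 3 leaves in a person with a single opiate-positive baseline visit.
- Exclusion 4 requires regular use, so irregular use falls outside it.
- Exclusion 7 is open-ended, but it is about medical conditions and its example is hepatic. Whether opiate abuse fits is arguable.
- Exclusion 15 is the closest. Opiates can be read into its drug classes, and any reported use within 30 days is enough. It does not name them, and it addresses use, not diagnosis.

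**Step 3: do the two eligibility reviews close it?** The PI review checks the same list. The physician review states no separate opiate rule.

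**Step 4: does urine testing at the drinking session close it?** Largely, for current use. Section V.3 (Alcohol-Drinking Paradigm) requires urine drug tests on arrival at each session and reschedules the session if they are positive. The baseline session is in Phase 2, before the first medication period in Phase 3, so it should go ahead only on a negative test. A second positive there would arguably also meet exclusion 3. Two limits apply: that section does not name the test panel (I assume it includes opiates), and a positive leads to rescheduling, not exclusion.

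**Step 5: who is left?** (a) A person with current opiate abuse whom reviewers do not place under exclusion 15. (b) A person with one opiate-positive baseline screen and a negative one afterwards.

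**The case against.** The strongest reply is that the exclusion is already in the protocol. Sections VI.2, IX.1 and IX.2 are current text. The first two say that the rule works through self-report and urine screens, which are the mechanisms of exclusions 15 and 3. Exclusion 2 is the general rule for other substances and agrees with the first of the two sentences quoted from Section IX.2. On this view the list only fails to repeat a stated rule. Adding a diagnosis would gain little, since the SCID is also an interview: a person who admits recent use is already out under exclusion 15, and one who hides it may hide it again.

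Much of this stands. Exclusion 15 probably does catch reported use, and it is no criticism that it relies on self-report when the safety text does too. The rescheduling rule already supplies most of what a repeat opiate screen before naltrexone would add, so no such step is proposed here.

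It does not remove the contradiction. Two sections promise exclusion for abuse and the list omits it. Exclusion 3 tolerates a positive that sits poorly with the aim in Section IX.2. Coverage through exclusion 15 depends on how each reviewer reads general wording.

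A reader might infer more than this, and the documents do not support it:
- That the plan has no opiate exclusion, or would knowingly give naltrexone to opiate users. The safety text says otherwise, and exclusions 2, 3 and probably 15 remove most such people.
- That anyone with an abuse diagnosis is at risk of withdrawal. The documents show no such risk for a person who truthfully reports no use in 30 days. For that person the only defect is the mismatch in wording.
- That one positive screen proves opiate use. An unconfirmed positive need not, and this part of the point rests on Section IX.2 alone.

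**Conclusion.** Wrong as written, with narrow scope. The textual contradiction is certain. The practical gap is small and is confined to the two groups in step 5. Its size cannot be given, because the documents report no rate of opiate abuse or of single positive screens among people who consent. The judgement that the gap is small rests on two assumptions: that reviewers usually read exclusion 15 as covering opiates, and that the urine panel at the drinking sessions includes them. If either fails, the gap is wider. No sample size, power, alpha or analysis figure changes. The point deserves correction because it concerns a safety exclusion for a drug that every subject takes and the correction is easy.

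**What to change.** Add one opiate-specific exclusion to Section VII.3, met by any of:

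1. current DSM-IV opiate abuse or dependence on the SCID already given at intake;
2. any self-reported opiate use in the 30 days before randomization;
3. an opiate-positive urine screen at any baseline visit.

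Then take opiates out of exclusion 3, so that its allowance for one positive visit applies only to cocaine, benzodiazepines and barbiturates. Exclusion 2 can stay as the general rule. The change should tighten the list, since all three safety statements point that way.

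The cost is a short text amendment. It uses the existing interview, self-report and urine screens and needs no new test. The downside is a few more screen failures, some from false-positive screens, at a rate the documents do not give.
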